Appendix B.	

STELLATE GANGLION BLOCKAGE IN COVID-19 POSITIVE PATIENTS
IRB#523-20-FB

Principal Investigator:

[name].
Assistant Professor
Director of Pain Clinics
Pain Medicine/Anesthesiology
University of Nebraska Medical Center

Supported by:

Department of Anesthesiology
University of Nebraska Medical Center

UNMC Nebraska Neuroscience Alliance COVID-19 Rapid Response Grants

NCT Number:

04445337

Brief Summary:

The proposed research plan will reflect the proof of concept of our modified stellate ganglion block in the human subject, following several key cardiac and pulmonary parameters leading to clinical benefit as well as the safety aspects of stellate ganglion blockade (SGB). Enrolling subjects will be enrolled from patients cared for in the COVID ICU/progressive care at Nebraska Medicine.

Patient eligibility will be determined based on the following criteria; Any patient between the ages of 40-75 with laboratory established COVID-19 infection (via rRT-PCR) requiring critical care in an intensive care unit, signs or symptoms consistent with ARDS, at least 2 of the following (respiratory rate ≥ 30 breaths per min, oxygen saturation at rest $\leq 93\%$, $\text{PaO}_2/\text{FIO}_2 \leq 200$ mm Hg, bilateral infiltrates on chest radiograph or CT not due to cardiac failure, requiring non-invasive or invasive mechanical ventilation.) Block randomization will be used to determine equal allocation to control (labs, nitric oxide levels +SOC) and intervention group (labs, nitric oxide levels, SGB procedure, perineural catheter 5 days). Once enrollment criteria are met, baseline assessments will be completed by the Acute Pain Service (APS). They will place SGB and manage intervention group for 5 days. Data collection will be collected through Day 5 of hospital stay, discharge information will be documented, and survival at 90 days via telephone to complete SF 36 questionnaire.

Section 1.0 Objectives:

To assess the safety, tolerance, oxygenation, lung and cardiac function, proinflammatory immune response and nitric oxide changes associated with the use of our modified SGB protocol in patients with ARDS due to COVID-19 disease.

Secondary (to be confirmed at later trial phase): To determine the association of use of our modified SGB protocol in patients with ARDS due to COVID-19 disease on: incidence of cardiac arrhythmias associated with ARDS, need and duration of use of mechanical ventilation and extracorporeal membrane oxygenation (ECMO).

Section 2.0 Introduction:

The novel coronavirus, now officially designated as severe acute respiratory syndrome coronavirus-2 or SARS-CoV-2 was first identified in Wuhan, Hubei Province, China in December of 2019. Since its identification, Coronavirus disease 2019 (COVID-19) has evolved into an international public health emergency. As is common for the coronavirus family, (SARS-CoV-1 and MERS), COVID-19 is associated with acute respiratory infection. The mortality of COVID-19 infection is mostly due to complications related to pneumonia and ARDS¹.

Strategies to mitigate ARDS and consequent multi-organ failure is in high demand. Currently, there are no FDA-approved treatments outside of supportive care for patients suffering from ARDS due to COVID-19. Unique to COVID-19 associated respiratory failure and ARDS is the early overproduction of proinflammatory cytokines. This exaggerated immune response or “cytokine storm,” is felt to lead to increased vascular hyperpermeability, multiorgan failure, and death. Many ARDS/lung injury patients manifest refractory hypoxia, cardiac arrhythmias and acute myocardial damage¹⁰⁻¹³. Cardiovascular complications such as circulatory failure are

frequently associated with COVID-19 ARDS and are associated with a poor outcome¹⁴. Case series have noted cardiac arrhythmias, cardiomyopathy, and cardiac arrest as terminal events in Covid-19¹⁵⁻¹⁷. Stellate ganglia block (SGB) is a common clinical intervention to treat both sympathetic nervous system overstimulation and refractory cardiac arrhythmia. Traditional chemo-neuromodulation paradigms employ a single SGB strategy deriving short-term (lasting a few hours to one day) control of sympathetically mediated symptoms, e.g., cardiac arrhythmias are controlled by temporarily blocking stellate neuronal activity with local anesthetics¹⁸⁻²⁰. Once the anesthetic effect is withdrawn, cardiac arrhythmias recur. We propose a modified SGB strategy utilizing a continuous infusion of medications instead of a bolus injection. We expect to achieve a lasting chemo-neuromodulating effect in COVID-19 ARDS patients reducing overall inflammation, improving pulmonary function, and reducing cardiac complications.

Preliminary Data: A notable innovation of our modified SGB approach is the addition of clonidine and dexamethasone to a local anesthetic (LA). The scientific rationale supporting this modification is derived from both the literature as well as work done here at UNMC by [name] (Figure 1).

[figure not shown]

Figure 1. A schematic of our hypothesis indicating how SGB with clonidine and dexamethasone (Dex) could have a beneficial effect on arrhythmia and cardiac complication in acute respiratory distress syndrome (ARDS).

Recent animal studies from [name] lab suggest macrophage activation in stellate ganglia plays a critical role in mediating acute lung injury-caused cardiac arrhythmia (Figure 2).

[figure not shown]

Figure 2. Representative immunofluorescence images (A) and summary data (B) showing increased number of Iba1-positive macrophages in the stellate ganglia (SG) in bleo-treated lung injury rats. TH, tyrosine hydroxylase, a SG neuron marker; DAPI, a nuclear marker. C, representative western blot images and mean data showing that IRF8 (a macrophage activation marker) expression was time-dependently increased in the SGs of 1-week and 4-week Bleo rats. (D), representative western blot images and mean data showing that the increased protein expression of IRF8 in the SGs of 4-week Bleo rats was largely prevented by minocycline (Mino).

Additionally, systemic administration of an anti-inflammatory medicine, minocycline, can largely block macrophage activation and arrhythmias in a bleomycin-induced lung injury rat model (Figure 3).

[figure not shown]

Figure 3. Original tracing (A and B) and mean data (C and D) showing the number of PVCs per 24 hours and their distributions over day and night in sham, Bleo, and Bleo+Mino rats at different time points (1w, 2w, 3w and 4w post Bleo). Data are expressed as mean \pm SE. n=5-9/each group. **P<0.01 vs. sham group, #P<0.05 and ##P<0.01 vs. Bleo group.

[name] findings support the novel concept that local delivery of anti-inflammatory/anti-macrophage medicine to/around the stellate ganglia may be a promising new therapy for treatment of inflammation-augmented comorbidities (especially cardiac) in acute lung injury/ARDS patients. To test this hypothesis in humans, we propose addition of two medications to the LA-SGB. Low dose dexamethasone will be added to ameliorate stellate ganglia inflammation directly. Additionally, based on [name] work, we will also add clonidine. This additive is supported in that 1) clonidine selectively stimulates α 2 adrenergic receptor and promotes the norepinephrine reuptake by cardiac sympathetic nerve endings²⁰⁻²² 2) clonidine has local anti-inflammatory effects via promoting apoptosis of leukocytes and switching pro-inflammatory macrophage to anti-inflammatory macrophage²³. In addition to testing, the beneficial cardiac effects of our modified SGB approach, we also aim to examine if SGB could also improve lung damage/inflammation as well as respiratory function in COVID 19 patients. This work is also previously performed in animal models. In septic rats,

SGB was able to attenuate sepsis related lung injury and decrease serum levels of TNF-alpha and IL-6³. In a direct lung injury model using rabbits, SGB showed decreased levels of TNF-alpha, IL-6 and IL-10 as well as decreased postmortem acute lung injury⁴. Human studies in trauma patients revealed immunological findings of decreased pro inflammatory cytokine production, and no negative effect on cardiovascular or pulmonary parameters.² Finally, in one small human study of patients undergoing one-lung ventilation, SGB was shown associated with increased plasma levels of nitric oxide and improved oxygenation⁵. In animal models, SGB was shown to improve pulmonary hypertension via NO production; oxygenation was improved as well.⁶⁻⁷ Several studies show nitric oxide can directly inhibit RNA synthesis, viral protein accumulation and virus released from infected cells. This was found in a variety of viruses, but specifically SARS. Not only was replication of the virus reduced, but NO was found to block SARS binding to the receptor host.⁸⁻⁹ We expect that the modified SGB strategy will achieve prolonged anti-arrhythmia and anti-inflammatory effects in COVID patients.

Study Rationale:

Available research indicates that an exaggerated immune response plays a key role in the cardiopulmonary pathophysiology of COVID-19. Preliminary data from previous studies at UNMC suggest that acute lung injury initiates robust and sustained macrophage activation in thoracic dorsal root ganglia and in stellate ganglia, resulting in increased cardiac and pulmonary afferent and efferent neuronal sensitivity. In the current proposal, we plan to validate a novel therapeutic strategy to treat coronavirus-induced cardiopulmonary symptoms and complications by local delivery of bupivacaine, dexamethasone, and clonidine to the stellate ganglia. Single injection and continuous infusion SGB have been safely utilized clinically and in many human studies.

Section 3.0 Eligibility Criteria:

Inclusion:

- Subject admitted to COVID ICU/progressive care, age 40-75 years old

Subjects must have + covid test with signs of impending respiratory compromise as identified by having at least 2 of the following:

- Respiratory rate ≥ 30 breaths per min
- Oxygen saturation at rest $\leq 93\%$
- $\text{PaO}_2/\text{FIO}_2 \leq 200$ mm Hg
- bilateral infiltrates on chest radiograph or CT not due to cardiac failure
- Requiring non-invasive or invasive mechanical ventilation.

Any patient with a + covid test and any cardiac tachydysrhythmia (excluding sinus tachycardia) will be included regardless of respiratory status. (Note: The broader inclusion of patients who have cardiac tachydysrhythmia is based on our prior experience and other reported beneficial antiarrhythmic effects of SGB in this patient group.)

Exclusion:

- Hemodynamic instability (>2 vasopressors)
- Heart rate < 60 beats per minute
- Systolic Blood pressure of less than 80 mmHg
- pre-hospital diagnosis of heart failure or fluid overload
- anatomical inability to perform block
- prior sympathectomy
- Patient currently enrolled in another clinical trial for COVID-19 or respiratory distress/ARDS
- Uncorrectable coagulopathy
- ECMO already engaged
- On Nitric Oxide
- Pre-existing multi-organ failure (>2 organ systems)
- Allergic to dexamethasone, clonidine, or bupivacaine.
- If female, currently pregnant or breast-feeding.
- Investigators determine the subject would be too unstable to participate in the study intervention.

If a woman of childbearing age is enrolled as a subject and there has not been a pregnancy test during their current inpatient stay, a urine or blood pregnancy test will be performed. Pregnancy will not be allowed for this study as the drug is absorbed systemically and there are known risks to the fetus.

Section 4.0 Registration Procedure:

A prospective block randomized phase I/II two arm unblinded trial of a modified SGB protocol incorporated into Standard of Care vs UNMC standard of care Only for ARDS COVID-19 patients.

Subjects and/or Legally Authorize Representative (LAR) will be approached while subject is in the ICU/progressive care. If subject is unable to participate in the consenting process, the LAR will be contact via telephone and/or video chat. Consents will be sent to LAR electronically. PI and/or Sub-I will be present for all consenting process regardless is the ICF process takes place in person or video digital presence.

The randomization will be done by using *Stratified Permuted Block Randomization* in which sequential trial participants will be subdivided into the strata as indicated by their age-groups ie; 40-59, 60-74, 75-85 years and thereafter allocated to study group via block randomization within the strata so that the balance between age groups between the two study groups stays close to equal throughout the trial.

Section 5.0 Treatment Plan of Research Design:

A prospective block randomized phase I/II two arm unblinded trial of a modified SGB protocol incorporated into Standard of Care vs UNMC standard of care Only for ARDS COVID-19 patients.

Sixteen subjects will be enrolled. Eight in the control arm and eight in the intervention SGB arm.

Subjects will be identified on the COVID unit. The study will be explained to the subject and if the subject wishes to voluntarily participate, the ICF will be signed. If the subject is unable to sign consent, the LAR consent will be utilized. If LAR is not present, an electronic link to the consent will be sent to the LAR via email.

The attending proceduralist will perform the SGB in the ICU/progressive care. ICU/progressive care nurse will provide patient monitoring and assistance during the procedure. Standard monitors and ACLS resuscitative equipment will be immediately available. A norepinephrine solution will be at bedside to treat potential hypotension associated with SGB. The SGB perineural catheter will be placed using standard sterile technique. Initial perineural bolus injection - clonidine 100 mcg, Decadron PF 5mg, and 0.25% bupivacaine 5 ml is delivered. A Cadd perineural infusion 0.2% bupivacaine will be initiated at 2ml/hr for 5 days. Acute pain service will discontinue infusion and remove the catheter after 5 days.

All adverse events and serious adverse events related to the SGB. All other adverse and serious adverse events, including death will be reported per IRB requirements. Laboratory analysis will be obtained at baseline (prior to block, baseline) and on day 1, day 3, and day 5. Labs include a cytokine panel (TNF-beta, IL-6, and IL-1 β), measurements of exhaled nitric oxide levels, and CRP (daily). Vital Parameter Analysis: Oxygenation, supplemental oxygen, type of respiratory support and need for mechanical ventilation, blood pressure i.e. hypotension requiring vasopressors and utilization of ECMO, heart rate, heart rhythm/new dysrhythmias, ICU/progressive care length of stay and discharge disposition will be collected from the EMR.

Control group: There will be no sham procedure for the control group. The control group will have nitric oxide levels performed once a day by a member of the research team. Lab draws will be drawn at the same frequency as the treatment group.

Treatment group:

The treatment group will have a SGB placed by the APS.

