Appendix A. Protocol for stellate ganglion blockade in COVID-19 patients.

ICU/progressive care RN will follow Med-27 NM policy for peripheral nerve catheter management. APS will utilize a similarly established standard of care in managing the catheters daily, for 5 consecutive days. This includes daily rounding on the patient to assess for signs of infection, muscle weakness, voice hoarseness, hematoma, intravascular migration, local anesthetic systemic toxicity, correct medication verification, verification of pump setting, evaluation for Horner's syndrome (expected), patient education, and proper dressing coverage.

Horner's syndrome refers to a constellation of symptoms that are associated with a stellate ganglion block. These include a decreased pupil size on the affected side, delayed reaction to light on the affected side, drooping eyelid and decreased sweating on the affected side. Increased temperature and vascular dilation are also noted on the affected side with stellate ganglion block.

Schedule of events: *treatment group only

Assessment	Screening: Visit-1	Baseline, Enrollment, Randomization : (Day 0)	Treatment Day 1	Treatment Day 2	Treatment Day 3	Treatment Day 4	Treatment Day 5	EOS Discharge from hospital	Follow-up: Day 90
Inclusion/Exclusion Criteria	X								
Informed Consent Form	X								
Enrollment/Randomization	X								
Demographics	X								
Eligibility	X								
Medical History	X								
Data Collection (Vitals ect)	X	X	X	X	X	X	X	X	
Acute Pain Service		X*	X*	X*	X*	X*	X*		
Stellate Ganglion Block		X*							
CRP		X	X	X	X	X	X		
TNF-Alpha		X	X		X		X		
IL-Beta		X	X		X		X		
IL-6		X	X		X		X		
Nitric Oxide Level		X	X	X	X	X	X		
Telephone Call									X
Concomitant Medications		X	X	X	X	X	X	X	X
Adverse Events		X	X	X	X	X	X	X	X

Section 6.0 Measurement of Effect:

We will be taking *measurement of the biomarkers indicative of oxygenation, lung and proinflammatory immune response and nitric oxide* - specifically,

[figure not shown]
- a) differences in mean/median values for SGB vs SOC will be assessed at each of the study designated time points for all the continuous biomarker measures - by assessing magnitude of difference and its 95% confidence level and testing differences for statistical significance at each of the time points;

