- b) Differences in mean/median values for SGB vs SOC will be assessed at treatment day 5 - adjusted for baseline levels
- c) Differences in changes from baseline levels for SGB vs SOC as measured by comparison in slope trends;
- d) Differences in frequency of adverse events for SGB vs SOC over the study period from treatment through 90 day of follow up;

Secondarily,

- e) Differences between SGB vs SOC in *frequency and time to occurrence of cardiac arrhythmias*;
- f) Differences between SGB vs SOC in frequency of *need for and duration of use mechanical ventilation and/or extracorporeal membrane oxygenation (ECMO)*;
- g) Differences between SGB vs SOC in survival experience over treatment period through 90 -day discharge follow up

Sample Size issues:

For power computations we assume that SGB will particularly have an impact in reduction of inflammatory response as measured by IL-6. Looking at a meta-analyses of IL-6 values [Ulhaq ZS, Soraya GV. Interleukin-6 as a potential biomarker of COVID-19 progression. *Med Mal Infect.* 2020;50:382–383. doi: 10.1016/j.medmal.2020.04.002. 2020/04/08] and picking the largest of studies of COVID patients [Qin C, Zhou L, Hu Z, Zhang S, Yang S, Tao Y, et al. Dysregulation of immune response in patients with COVID-19 in Wuhan, China. *Clin Infect Dis* 2020, <http://dx.doi.org/10.1093/cid/ciaa248> [pii: ciaa248].], we estimate the overall mean (SD) IL-6 for COVID-19 patients to be 21 pg/mL (30.1). Using these estimates we see that a sample of 16 patients equally randomized into SGB (n=8) and SoC (n=8) would provide sufficient power to observe magnitude of differences in mean of IL-6 from as small as about 50 pg/mL and larger with 80% power at the 5% significance level assuming 2-sided hypothesis testing. (see Power Figure). The study [Liu MH, Tian J, Su YP, Wang T, Xiang Q, Wen L. Cervical sympathetic block regulates early systemic inflammatory response in severe trauma patients. *Med Sci Monitor.* 2013;19:194–201.], indicates that SGB is capable of eliciting reductions of IL-6 between groups and from baseline of magnitudes of greater than 100 pg/mL within 72hrs of first injection.

Section 7.0 Study Parameters:

Baseline Assessments

- Current Fio₂/PaO₂ ratio
- Current type of ventilation and oxygen use
- Current production of nitric oxide via Niox
- Current blood pressure and heart rate parameters
- Labs: IL-1beta, TNF-alpha, IL-6, ABG, CRP
- Chest x-ray
- Need for mechanical ventilation or other support

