Initial perineural bolus injection will include clonidine 100 mcg, decadron PF 5mg, and 0.25% bupivacaine 5 ml.

Perineural catheter:

Infusion of 0.2% bupivacaine will be initiated at 2ml/hr for 5 days.

All medications are FDA approved. Standard orders for perineural blocks will be entered into the EMR system. Pharmacy responsible for ICU/progressive care will dispense orders for the medication used in the SGB. Pharmacist in ICU/progressive care will fill Cadd pump infusion catheter once per day per standard procedure in the ICU/progressive care.

Section 9.0 Adverse Event Reporting Guidelines:

The initial procedure will be stopped and the patient will be withdrawn if any of the following occurs; vasopressor or unresponsive hypotension, intrathecal injection, pneumothorax, expanding hematoma, allergic reaction, or cardiac arrhythmias. For continuous infusions, the catheter will be removed and the patient will be withdrawn if any of the following occur: local systemic toxicity, seizure, catheter migration to intravascular or intrathecal space, expanding hematoma, vasopressor unresponsive hypotension, symptomatic bradycardia, insertion site infection. Any adverse events will be treated with Nebraska Medicine standard of care procedures. Subjects can also voluntarily withdraw at any time. The PI can also withdraw any subject that is not felt to be a suitable candidate for the study.

Serious adverse events directly related to block will result in withdrawal. Directly block related serious adverse events include: local systemic toxicity, seizure, serious allergic reaction, expanding hematoma, or catheter migration to intravascular or intrathecal space, insertion site infection. As well, patients will be withdrawn if the patient develops medication unresponsive bradycardia or hypotension. This may not be directly related to block but discontinuation of infusion may facilitate resuscitation of patient. Expected complications may include voice hoarseness, ipsilateral eyelid drooping, mild pain at site of catheter, and blurred vision. Occurrence of expected complications will not result in withdrawal from study unless demanded by the patient.

Section 10.0 Statistical Considerations:

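### The observation window for arrhythmia, ventilation and ECMO is inconsistent: the Brief Summary and Section 7.0 end at Day 5, about when the catheter comes out, while other sections may run to discharge

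*Combined protocol and SAP*

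**What the plan says.** **Objectives and measures.** Section 1.0 lists among its secondary aims "need and duration of use of mechanical ventilation and extracorporeal membrane oxygenation (ECMO", together with the incidence of arrhythmias. Section 6.0 repeats these as item (e), "frequency and time to occurrence of cardiac arrhythmias", and item (f), need for and duration of ventilation or ECMO. Items (d) and (g), adverse events and survival, state a 90-day window. Items (e) and (f) state none.

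**Window.** The Brief Summary says "Data collection will be collected through Day 5 of hospital stay, discharge information will be documented"; the same sentence goes on to a 90-day telephone contact for survival and the SF-36. Section 7.0 itemises telemetry arrhythmias, FiO2 and vasopressor use for Days 1 to 5 and then goes straight to Day 90. In the schedule of events, the row "Data Collection (Vitals ect" is marked from screening through Treatment Day 5 and once more at discharge, with no content given for the discharge mark. Section 5.0 takes type of respiratory support, ECMO use, new dysrhythmias, length of stay and discharge disposition from the EMR and gives no end date.

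**Treatment period and rationale.** Section 8.0: "Infusion of 0.2% bupivacaine will be initiated at 2ml/hr for 5 days". Section 5.0 has the catheter removed after those 5 days. The Introduction says of the ordinary single block: "Once the anesthetic effect is withdrawn, cardiac arrhythmias recur". Of the modified block it says: "We expect to achieve a lasting chemo-neuromodulating effect in COVID-19 ARDS patients".

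**Analysis.** Section 10.0 names time-to-event methods for occurrence of arrhythmia, need for support, and survival. It gives no method for duration, no censoring time and no handling of death.

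**The concern.** Duration of ventilation or ECMO can be measured only if observation continues until support ends. A 5-day window is short for this population, which includes patients already on ventilation at entry, and a short window compresses any difference between arms.

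For arrhythmia the difficulty is timing. The case for a continuous, modified block is that its effect should outlast the drug. Systematic arrhythmia assessment that ends about when the infusion ends cannot separate an effect confined to the infusion from one that persists. Section 10.0 intends to carry suggestive trends into a phase IIb/III trial, so the distinction bears on what that trial would be designed to show.

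**Working it through.** The plan states no figure for this point, so there is none to reproduce. The check has two parts.

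**1. The sections side by side**

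| Place | Ventilation / ECMO | Arrhythmia | Ends |
|---|---|---|---|
| Brief Summary | general data collection | general data collection | Day 5 of hospital stay, plus unspecified discharge information |
| Section 7.0 | type of and need for ventilation at baseline only; FiO2, PaO2 if available, and blood gas if ventilated on certain days; ECMO not named | telemetry, Days 1–5 | Day 5, then Day 90 (survival, SF-36, adverse events, ongoing issues including oxygen use) |
| Schedule of events | one general data-collection row | same row | one mark at discharge, content undefined |
| Section 5.0 | from EMR, no start/stop dates | from EMR, new dysrhythmias | not stated |
| Section 6.0 (e), (f) | duration compared | frequency and time to occurrence | not stated |

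The block is placed on Day 0 and the infusion runs for 5 days. The Day 5 list still records infusion rate and evidence of ongoing block, so Day 5 is in effect an on-treatment assessment. No itemised arrhythmia assessment and no biomarker sample falls between catheter removal and discharge.

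The Summary counts days of hospital stay, whereas the schedule counts treatment days from Day 0 (randomisation). The two differ for anyone not randomised on admission.

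**2. What a Day 5 cut would do to duration**

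The documents give no ventilation durations, so these are assumptions. For exponential durations with rate λ = ln 2 / median:

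- untruncated mean = 1/λ
- share still on support at Day 5 = exp(−5λ)
- mean observed within 5 days = (1 − exp(−5λ))/λ

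| Median (days) | λ | Mean (days) | Still on support at Day 5 | Mean within 5 days |
|---|---|---|---|---|
| 14 | 0.0495 | 20.20 | 0.781 | 4.43 |
| 10 | 0.0693 | 14.43 | 0.707 | 4.23 |
| 7 | 0.0990 | 10.10 | 0.610 | 3.94 |

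- Medians 10 vs 7: true mean difference 14.43 − 10.10 = 4.33 days. Visible within 5 days: 0.28 day, which is 0.28/4.33 = about 6.5%.
- Medians 14 vs 7: true mean difference 20.20 − 10.10 = 10.10 days. Visible: 0.49 day, which is 0.49/10.10 = about 4.8%.

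Over a wider range of assumed means m, using exp(−5/m) and m(1 − exp(−5/m)):

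| m (days) | 3 | 5 | 7 | 10 | 14 | 21 |
|---|---|---|---|---|---|---|
| Still on support at Day 5 | 19% | 37% | 49% | 61% | 70% | 79% |
| Of 8 patients | 1.5 | 2.9 | 3.9 | 4.9 | 5.6 | 6.3 |
| Mean within 5 days | 2.43 | 3.16 | 3.57 | 3.93 | 4.20 | 4.45 |

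The "of 8" row supposes that all 8 patients in an arm are on support from Day 0. A sevenfold range in true mean duration is compressed to 2.4–4.5 days.

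**The case against.** A reader of the Summary and Section 7.0 might infer that all data stop at Day 5 and that duration cannot be measured. The documents do not support that. The Summary sentence goes on to discharge information and 90-day survival. The schedule marks data collection at discharge. The Section 5.0 EMR list includes length of stay and discharge disposition, which cannot be known on Day 5 for anyone still in hospital. Support dates may therefore be recoverable. This part of the objection stands.

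A reader might also infer that the arrhythmia objective fails. It does not: incidence can be estimated over Days 0–5. Persistence after withdrawal is an expectation in the Introduction, not a listed objective, and nothing in the plan says that Day 0–5 data will be reported as proof of a lasting effect. Adverse events are collected to Day 90, so some later arrhythmias would be recorded. However, such reports depend on someone judging the arrhythmia to be an event, and in an unblinded trial that may differ between arms.

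The remark about hospital days could be pressed further, to say that a patient randomised on hospital day 4 is observed for one treatment day. The schedule and Section 7.0 both count Treatment Days 1–5, so this is loose wording to correct, not a planned one-day window.

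Finally, the comparison is weak whatever the window. Suppose all 8 per arm are ventilated from Day 0, with medians 10 vs 7. The log hazard ratio is ln(10/7) = 0.357. With complete follow-up (8 events per arm) its standard error is √(1/8 + 1/8) = 0.50, and two-sided 5% power is about 11%. With a 5-day cut, expected events are 8 × 0.293 = 2.3 and 8 × 0.390 = 3.1, the standard error is about 0.86 and power is about 7%. Censored data still estimate a hazard ratio under this model, and the protocol itself defers these outcomes to a later phase. This stands, and it limits the point to what the trial can describe. It does not make an undefined window acceptable for a measure the plan says it will compare.

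**Conclusion.** The concern holds as a conflict and an omission. The Summary and Section 7.0 end at Day 5, while the schedule and Section 5.0 may extend to discharge, without saying what is recorded there or with which dates. No section states the window, censoring time or handling of death for duration of support.

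The size of the effect is conditional. If the Day 5 limit is followed and durations are exponential with medians of 10 and 7 days, 71% and 61% are censored and a 4.33-day difference shows as 0.28 day. For assumed means of 3 to 21 days the censored share runs from 19% to 79%. None of these durations comes from the documents, and the hard cut is only one reading of them.

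For arrhythmia, under the same reading, systematic assessment covers essentially the infusion period alone. The trial can describe incidence up to Day 5, but has no structured measurement of what follows removal. That is worth correcting because it is cheap, even though these outcomes are exploratory.

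**What to change.** - **Brief Summary:** replace the Day 5 hospital-stay limit with a window counted from randomisation (Day 0).
- **Sections 5.0, 6.0 (e)–(f) and 7.0, and the discharge column of the schedule:** state that dated start and stop of non-invasive ventilation, invasive ventilation, ECMO and each telemetry-documented arrhythmia are abstracted from the EMR from randomisation to hospital discharge or death, in both arms.
- **Section 10.0:** analyse duration of support with a stated censoring time and with death as a competing event. Report arrhythmia separately for Days 0–5 and after Day 5, in both arms.
- **Biomarkers:** keep the Day 0–5 sampling and limit biomarker conclusions to effects during the infusion.

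The cost is protocol wording and additional EMR abstraction for 16 patients, with no new procedure or blood draw. Telemetry will be less uniform after Day 5, so the later arrhythmia data should be presented with that caveat. With 8 patients per arm the comparison remains exploratory.
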